2.3 RISK/BENEFIT ASSESSMENT

2.3.1 KNOWN POTENTIAL RISKS

In general, the potential risks are considered minimal. These potential risks include:

Potential risks of casting/splinting: While a child's less impaired arm is constrained, she/he may have some initial negative feelings and may require a period of adjustment (usually <24 hr) to the constraint. These may include feelings of anxiety or fear because the cast is something that is new and perhaps unknown to the child; frustration or anger about having the "good arm and hand" restrained and thus limiting the child from some typical activities using this upper extremity; and possible swelling (if the constraint were not properly applied) or skin irritation or an allergic reaction to the casting or splinting material. Parents will be informed about all potential risks. Any casting-related problems would be corrected within 24 hrs.

A child's initial reaction during the first 24 - 48 hours of being casted may include mild distress; for most children, however, their reaction is one of rapid adjustment, curiosity, and then within a day or two, they seem to ignore the cast. The casting procedure is usually constructed while the child interacts with the parent or watches a fun videotape. It is made with a very lightweight material known as Focused Rigidity casting that allows one side of the cast to be fairly rigid while allowing the other side of the cast to maintain some flexibility. This material allows for a very lightweight cast which immobilizes and restricts use but is not as restrictive as a more traditional and heavier casting material designed to fully immobilize joint and bone placement (e.g., for a broken bone). The cast is constructed so that it can be readily removed, and parents are told how to remove this if an urgent situation arises. We ask parents not to remove the cast, however, without calling the local treatment team. Parents are given the therapist's name and 24-hour (mobile) telephone number, and at least one additional name and phone number of another clinician on the research team; they are strongly encouraged to call *at any time* during the course of treatment with any concerns about the cast or any other aspects of treatment and their child's well-being. If needed, we send someone to the child's home as soon as possible.

We will systematically remove the cast (that is univalved when fabricated) once a week to check on skin integrity. If any irritation or cuts appear, we treat these and, as needed, provide additional padding or adjustment of the cast before returning it. During this weekly check, we also wash the child's arm and hand, test range-of-motion, and spend about 10-15 minutes having the infant use the arm and hand in typical ways, such as manipulating a toy or object. If any loss of function is detected or suspected, this would be reported as an Adverse Event or Serious Adverse Event complying with the University of Cincinnati Human Research Protection Program Policy 11.02. (To date, this has never happened.)

Potential risks of intensive treatment: We anticipate that all of the children enrolled in this RCT will have had some prior experience with occupational and/or physical therapy that is focused on trying to improve their use of the hemiparetic side of the body. We consider the risks involved with this study to be minimal, but they may include the following: a possible period of adjustment to a new therapist, because some children are naturally shy or slow-to-warm-up; and experiencing fatigue or frustration because many of the tasks that the therapist will be using to engage the child necessitate that the child be an active partner in making effort and repeatedly practicing certain new movements and skills. For most children, the U&CT therapy they typically receive occurs in a session that lasts about 50-60 minutes, although some may have had sessions that last as long as 90-120 minutes. The I-ACQUIRE treatment we have developed and will administer in this RCT emphasizes that the tasks used in therapy should primarily be ones which are fun, interesting, and practically useful for the child. For almost all young children, parents can identify favorite toys, objects, or activities to include in the therapy goals. Examples of objects and activities that have wide appeal are using bubble wands to blow bubbles, activity boxes with fun and surprising results from pressing and pulling, books, puzzles, different sizes and types of balls, and games that involve reaching and targeting a goal. In addition, everyday self-help skills of eating, drinking, and

dressing are natural activities ideal for implementing the therapy cycles that have the child initiate a movement, receive reinforcement and feedback, and then repeat and eventually refine their upper extremity skills. The therapists are trained and instructed to end or change activities when a child shows high or sometimes even moderate levels of fatigue or frustration – usually lasting more than 2 or 3 minutes. However, it is undeniable that there are some periods of openly expressed frustration and fatigue that infants show while they are “trying so hard” to do something that does not happen easily. Because the therapist can shift activities throughout the course of a treatment session, such as returning to earlier (more successful) activities, and can provide periods of reassurance with soothing interactions that help infants to calm negative emotions and redirect attention, the I-ACQUIRE therapy sessions are most often interesting, pleasant, and productive. Whenever needed, as observed and suggested by the therapist or parent, the child may take a nap. When naps occur, the therapy session is adjusted to make up for any lost active therapy time.

We actively monitor the progress of each child in therapy. The therapists maintain daily detailed logs on a standardized form, and these are reviewed by the Treatment Implementation Center weekly, with feedback provided to the therapist. Parents are encouraged to contact the local site study coordinator or the PI with any concerns, questions, or suggestions.

Potential risks of treatment in naturalistic settings: Because I-ACQUIRE is delivered in naturalistic environments with families often involved, therapists may sometimes be exposed to family dynamics that do not occur as much in traditional hospital or clinical settings. The family thus may sense intrusion or a loss of privacy; sometimes families may feel embarrassment or shame related to something highly sensitive that may occur when the therapist is in their home.

Therapists will be instructed to report all instances of unusual circumstances that may be a cause for concern about the health, safety, or well-being of the treated child (or any other child on this premise). This report will comply with the reporting requirements of the University of Cincinnati Human Research Protection Program Policy 11.02 for reporting unanticipated problems involving risk to human subjects or others, adverse events, and other problems. We will provide formal training to all project personnel about local guidelines at all clinical sites for reporting suspected child neglect and abuse. Parents also are informed -- verbally and in writing -- when they volunteer to be in the study that we must adhere to local policies about reporting observed or suspected child maltreatment.

Behavioral Assessments: All children in this trial will have likely been seen for clinical assessments that are similar to what children will be asked to do during our outcome assessment battery. The standardized assessments primarily involve having the child manipulate small objects and toys, demonstrate gross motor skills, and show their abilities related to age-typical self-help activities, problem-solving, or knowledge about language and social interactions. The primary risks are slight fatigue and frustration at not being able to complete a task. The administration procedures for the tools selected are ones that take into account the needs and interests of children. The assessment session is play-like in its structure and there are no negative judgments or expressions of disappointment about the child’s performance. All of these standardized tools have explicit protocols for the non-completion of items and stopping rules for more difficult items. These protocols will be followed and if signs of undue stress occur, the assessor will offer the child a break, a snack (with parent approval), or may choose to end the session. (Many of the assessments are included in NINDS recommendations for Common Data Elements for Stroke or for Cerebral Palsy and/or the NIH toolbox.)

Parental Reporting: A potential risk associated with the standardized parental reporting about their child involves the possibility that a parent becomes more aware of limits the child may demonstrate due to the targeted and specified questions about their child’s developmental progress and arm and hand use. Parents will be encouraged to ask questions brought up by the reporting and they will receive appropriate information in response to their questions and/or directed to reliable sources to obtain information.

2.3.2 KNOWN POTENTIAL BENEFITS

There is the potential for many or even all of the children participating in this proposal to receive substantial benefits that are detectable during and soon after therapy is provided, and these benefits may endure (and even

increase) for many months after therapy ends. The benefits of participation are anticipated based on the published results from previous RCTs, published clinical cases, and data analyses of two large clinical research cohorts. These likely benefits include but are not limited to increased movements in the hemiparetic arm and hand, increased bimanual skills, and increased coordination and functional skills with the hemiparetic arm and hand. These improvements have been associated later with children participating more in daily activities and attempting an increased number of new tasks. Since the children will be very young, there is also a possible benefit that increased awareness and abilities with the hemiparetic arm and hand will produce a base of functional abilities that will naturally allow them to continue and build new skills in other domains of functioning as they become older.

2.3.3 ASSESSMENT OF POTENTIAL RISKS AND BENEFITS

At the present time, there is insufficient knowledge about the efficacy of I-ACQUIRE for children with PAIS. The results from this adequately powered RCT will help to resolve clinically and theoretically important issues by providing much needed information to inform treatment recommendations and insurance coverage. Because there are minimal risks and many potential benefits to the children, we think the benefits outweigh the associated risks.

3 OBJECTIVES AND ENDPOINTS

OBJECTIVES	ENDPOINTS	JUSTIFICATION FOR ENDPOINTS
Primary (Aim 1)		

Determine the efficacy of I-ACQUIRE at 2 dosage levels compared to U&CT to increase upper extremity skills on the hemiparetic side both at End of Treatment and 6 mos Post-Treatment.
	
The primary efficacy outcome is measured by the Emerging Behaviors Scale (EBS). A favorable outcome is defined as a gain of ≥ 7 new EBS skills above baseline both at the End of Treatment and 6 mos. Post-Treatment Assessment.
	
Because I-ACQUIRE is a highly intensive and expensive treatment, we think the primary outcome must be large and sustainable – i.e., lasting at least 6 mos post-treatment. Although short-term gains may have some clinical benefit, we deem these insufficient to recommend adopting I-ACQUIRE as standard-of-care for children in this age range with PAIS.

Secondary (Aim 2)		

Determine the efficacy of I-ACQUIRE at 2 dosage levels compared to U&CT to improve use of the hemiparetic upper extremity in bimanual activities.
	
The secondary efficacy outcome is assessed by mean increases in Mini AHA scores in the 3 treatment groups at both the End of Treatment and 6 mos. Post-Treatment Assessment taking into account their baseline scores.
	
The Mini AHA assesses how well a child uses the hemiparetic upper extremity as a “helper arm and hand” in a range of age-typical bimanual activities, recognizing that the function of being a “helper arm and hand” is of clinical and practical value.

Exploratory (Aim 3)		

Explore the association between I-ACQUIRE treatment at Moderate and High Doses and gross motor development and cognition (i.e., examples of cross-domain effects of treatment).
	
If and only if I-ACQUIRE shows efficacy for primary and/or secondary outcomes, we will conduct exploratory analyses about cross-domain effects assessed by the Gross Motor Function Measure-66 and the Bayley-4 Cognition subtest at baseline, post-treatment, and 6 mos. post-treatment. (Other cross-domain changes amenable to exploratory analyses include Language as measured by Bayley-4 and the MacArthur-Bates Scales of Communicative Competence).
	
Prior small-scale trials reported cross-domain effects after treatment. Here we posit that improved upper extremity competency will increase child exploration and learning, with detectable benefits for at least some children in gross motor, language, and cognitive domains.

4 STUDY DESIGN

4.1 OVERALL DESIGN

The proposed study is a Phase III trial powered to determine efficacy of two different doses of I-ACQUIRE for children 8 to 24 months old with PAIS and hemiparesis. The design is a prospective RCT in which 240 children will be randomly assigned to one of 3 treatment groups (N=80 per group): 1) Moderate Dose I-ACQUIRE (3 hrs/day, 5 day/wk X 4 wks), 2) High Dose I-ACQUIRE (6hrs/day, 5 days/wk X 4 wks), or 3) Usual and Customary Treatment (U&CT). I-ACQUIRE will be delivered by protocol-trained therapists and monitored weekly for dosage and treatment fidelity; U&CT will be provided by community therapists with dosage and approaches documented weekly. All primary and secondary efficacy outcomes rely on blinded assessments at baseline, end of treatment, and 6 mos post-treatment. Exploratory outcomes and supplemental clinical measures may provide valuable additional data about development and health in this sample of children with PAIS.

There will be a second phase of the I-ACQUIRE Study for the children who had been randomly assigned to Group 3 (Usual and Customary Treatment). Their parent(s) may choose to enroll (via a new IRB-approved consent process) to have their child randomly assigned to receive either the Moderate or High Dose I-ACQUIRE treatment. This will occur after the 6-mos Post-Treatment Assessment from the primary phase. Outcome data from this second or crossover phase of the study will not be used in the primary data analysis for this trial but will be available for exploratory and post hoc data analyses.

4.2 SCIENTIFIC RATIONALE FOR STUDY DESIGN

PAIS is a serious event that can produce lifelong severe impairments: the most prevalent impairment is hemiparesis. Of high significance is that there have been no randomized controlled trials (RCTs) of CIMT protocols for this clinical population of children and no reported trials of CIMT for children under 2 yrs old. Multiple independent reviews of other therapy interventions for infants and toddlers conclude most are ineffective, some yield small magnitude benefits, few show enduring benefits. Similarly, no RCT of CIMT has focused on children with a diagnosis of PAIS. This matters because i) children under 3 yrs old differ in attention span, motor development, and learning modes from older children; ii) children with PAIS may differ clinically from the general hemiparetic CP population; and iii) plasticity of brain function after injury may relate inversely or differently to the child's age or stage of development.

Justification for age range of children in this trial: Typical UE development is rapid in the first 3 years. Bimanual skills emerge at 6 - 8 mos when a child holds an object with both hands and easily transfers it from hand to hand. The infant practices these bimanual skills so by ≈10 mos. the infant shows symmetrical movements (e.g., banging objects together, clapping). From 12 - 24 mos., the child acquires differentiated bimanual skills that permit one hand to hold an object while the other manipulates it. This milestone affects acquiring many other skills (e.g., holding a bowl and scooping food, stabilizing a bottom block while stacking others, placing marks on a paper held by one hand). Soon after, the child discovers that simultaneous hand movements can be separated and coordinated to achieve a wide array of functions from advanced toy play to self-feeding, turning pages of a book, dressing/undressing, and moving through space. With increasing age and opportunities, the child combines and refines upper extremity skills to engage in more complex and challenging activities in a variety of play, exploration, and self-help areas. Accordingly, 8 to 36 mos represents an ideal age window for I-ACQUIRE. (We found that 6 and 7 mos olds are a bit young for intensive shaping of UE skills.) Note: An additional benefit of focusing on this young age range is that this corresponds with the federal and state legal definition for "early intervention" defined as "birth to 2" that goes up to the child's third birthday and entitles to the child to provision of appropriate services for developmental delays and disabilities (under the federal and state IDEA regulations).

4.3 JUSTIFICATION FOR DOSES

We originally selected a 6-hr daily session because this comprises a large portion of the waking day, similar to the time infants and toddlers spend in childcare, early intervention programs, or school. This is the most tested

dosage for a “signature form” of pediatric CIMT¹⁷ and we know infants and toddlers tolerate (and often enjoy) this 6-hr dose (see Prior Studies). We selected other dose - the 3-hr dose – because it is similar to a half-day session in childcare, early intervention, or school. Both practically and clinically, the difference between 3 and 6 hr is large in terms of therapy cost and time demands on therapists and families. We did not select an even lower dose because we know of no evidence that this can produce benefits that are comparable to the large effect sizes reported in Prior Studies (many are much smaller or non-existent).^{37-39,41,43,125} Theoretically, the 6-hr dose may promote a stronger habit pattern of using the hemiparetic UE and, resultantly, produce larger and more enduring effects by 6 mos post-treatment than the 3-hr dose. Alternatively, if the 3-hr dose can produce significant, large, and enduring benefits, this would be important new information to inform the vigorous debate about the different high-dosage levels and reduce the cost of delivering I-ACQUIRE to eligible infants.

4.4 END OF STUDY DEFINITION

End of Study for the Primary Phase 1 is defined as after completing the 6 mos. Post-Treatment Assessment after the child received one of two dosages of I-ACQUIRE treatment or U&CT. In the second Crossover Phase, for those children who were in Group 3, Usual and Customary Treatment, the end of study will be after completing the 6 mos. Post-Treatment Assessment after receiving I-ACQUIRE.

5 STUDY POPULATION

5.1 INCLUSION CRITERIA

Inclusion Criteria: child will be 8 - 36 mos. old at time when study treatment during the primary Phase 1 will be delivered; have a diagnosis of Perinatal Arterial Ischemic Stroke (PAIS) with parent permission to provide the child’s clinical MRI to the study; hemiparesis; and parent(s) willing to participate in the home therapy component. At least one parent must be English-language proficient and be the parent who will take a lead in interacting with study staff and completing self-administered forms and interviews in English. (Note: for the crossover second phase, children from the U&CT group may be older than 36 mos. when they receive one of the two doses of I-ACQUIRE treatment.)

5.2 EXCLUSION CRITERIA

Exclusion Criteria: medical or sensory condition(s) that prevent(s) full therapy participation (e.g., frequent uncontrolled seizures, fragile health); received modified CIMT with a dose of at least 2 hrs/day for ≥10 days (Lower modified CIMT doses are permitted.); received botulinum toxin in past 3 mos, or baseline EBS score >24 points. If a child is a ward of the state or other agency, the child will not be eligible. NB: botulinum toxin or another form of CIMT cannot be administered until after the 6 mos Post-Treatment Assessment has occurred. (Note: an EBS score >24 points would be extremely rare in this age group and clinical population. It is an exclusion criterion because a child would be precluded from reaching the study primary outcome threshold of a gain of 7 or more EBS points. However, the EBS baseline score is not known until the Baseline Assessment is completed and scored centrally at the I-ACQUIRE Assessment Center at OSU.)

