Establishing a valid and reliable threshold for clinically meaningful benefits of treatment. Recently, our team proposed a systematic approach to estimate clinically meaningful gains, a relatively new endeavor in pediatric rehabilitation. First, we looked at approaches used in other rehabilitation trials (mostly adults).⁹⁷⁻⁹⁹ Next, we studied available EBS data for individual subjects in Phase I and II trials and our clinical database, along with other outcome measures, including therapist and parent ratings and observations. We examined a variety of thresholds, to understand whether there was an amount of gain (either an absolute number of new skills or a percent improvement score) that correctly differentiated patients whose parents and therapists did or did not consider their outcomes clinically meaningful. Consistently across studies and in the clinical database, a gain of 7 new EBS skills better coincided with parent impressions of substantial benefits compared to a % gain (even attempting % gain thresholds adjusted for age or baseline scores) Our process included discussions with rehabilitation experts and compiling validity (face validity, cross-tool validity, and predictive validity) and reliability (inter- and intra-rater >85%) data for EBS items (from multiple standardized tools). Other corroborating evidence for the EBS threshold was that children who met the criterion used their hemiparetic UE more often daily and in a wider array of age-normative activities (e.g., self-help, games, social interactions, and object manipulation).

The proposed threshold for clinically meaningful gain at the individual level has support from our prior trials and clinical database since the mean gain scores exceeded this in all prior studies. Face validity derives from considering that gaining at least 7 new core UE skills in just 4 wks, and maintaining at least this many at a later timepoint, represents about one-fourth (23.3% precisely) of the 30 item EBS total. This magnitude gain occurred for subjects with baseline EBS scores as low as 0 and as high as 23 (higher scores are rare for patients seeking CIMT). As **Figure 2** shows, 25 of 27 treated infants had EBS gains ≥ 7 .

Figure 2: Number of New Skills Gained on the Emerging Behaviors Scale (EBS) for 27 Infants with Hemiparesis after Receiving High Dose I-ACQUIRE

Ongoing multi-site RCT of I-ACQUIRE for infants with hemiparetic CP: Baby CHAMP (Study 6).

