8 STUDY ASSESSMENTS AND PROCEDURES

8.1 EFFICACY ASSESSMENTS

Primary Outcome MEASURE: The Emerging Behaviors Scale (EBS). The EBS is a standardized tool developed for pediatric rehabilitation research in hemiparesis. The rationale for this tool is that all young children, including those with hemiparesis, need to acquire a repertoire of essential upper extremity (UE) skills that are used frequently every day during play, self-help, object manipulation, and social communication. Without a sufficient number of these critically important UE skills, a child's future progress will be delayed and will lead to increasing impairment over time. The EBS thus represents a foundational base of core UE skills that extend into later ages. The EBS tallies the number of core skills (0 to 30) with the hemiparetic UE. (Note: once an infant acquires an early version of each skill, therapy focuses on improving that skill – e.g., ease, accuracy, speed, and integration with other skills into complex sequences). Items on the EBS appear as part of standardized tools (e.g., Bayley-4, Peabody Scales of Motor Development-2, the QUEST, NIH Toolbox). A unique feature of the EBS is the requirement that the child display each skill at least twice. Coding is completed by the blinded Central Assessment Core staff based on the videotaped session that includes the full Bayley-4, the Mini AHA, a snack break, and interactions with the assessor and parent at the start and close of the session. The parent ratings on the IMAL can be used as a source of one of the two times the skill was documented. All EBS items have high face and content validity and inter-rater reliability established on at least 3 standardized tools. Most have high predictive validity for the child's future performance on the same or similar items.

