The primary efficacy outcome is defined as gaining and retaining ≥ 7 new EBS skills above baseline EBS score at the End of Treatment and 6 mos Post-Treatment Assessments. Rationale and supportive evidence for the proposed criteria for a minimal clinically important outcome: For the past several years, we have engaged in efforts to identify a minimal clinically meaningful improvement on the EBS. We have reviewed outcomes for subjects in prior trials and our clinical database; studied clinical thresholds in other rehabilitation trials and goal-setting in therapy (often 5 – 10% gains); obtained input from pediatric OTs, PTs, and physiatrists; compared several thresholds that vary for subject age or baseline score; and cross-checked EBS scores with parent ratings, observations, and therapist logs of child progress

We recognize that a single dichotomous primary outcome has limits – notably, reduced detail about the precise magnitude of change and its slope over time. Finally, we selected the dichotomous outcome because: i) we think establishing pre-specified minimum high expectation for gaining and then maintaining a large number of new skills is justified, given the high cost of this time-intensive treatment. That is, if the gains were only short-term, parents and clinicians would likely be disappointed that benefits are merely transitory; and ii) we think the dichotomous outcome is easier for clinicians and parents to understand than a distribution-based or individualized outcome that is difficult to understand (because the EBS tool itself and the meaning of the range of scores are not widely known). The threshold of gaining ≥ 7 new EBS skills can be equated with about one-fourth of the entire EBS repertoire; further, all infants in the I-ACQUIRE trial and most infants with PAIS will have baseline EBS scores that allow them to acquire this many new skills. Our analyses affirm that this simple,

dichotomous outcome works well across the entire EBS continuum to classify those with and without a favorable treatment outcome. In our earlier studies, patients with divergent EBS baselines showed mean EBS gains ≥ 7 new skills. We are not certain, however, that a gain of only 6 EBS skills has no clinical meaning to an infant or parents.

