We further note that children with a baseline EBS of 24 or higher are excluded from the trial in terms of testing the primary efficacy outcome, because this would preclude achieving the study threshold. (Based on prior clinical trials and clinical research, a baseline EBS score of 24 or higher would be extremely rare. We further note, however, that we think the I-ACQUIRE treatment could possibly result in meaningful improvement for such a high functioning child, although the choice of the EBS as the primary outcome measure does not allow for fully capturing such potential benefits.)

Secondary Outcome MEASURE: The Mini-Assisting Hand Assessment (Mini AHA). The Mini AHA is a new tool that rates how well a child engages the hemiparetic UE as a “helper” in bimanual activities, recognizing that children with hemiparesis are unlikely to use their hemiparetic UE as their dominant E. The Mini AHA has high inter-rater reliability. A Rasch measurement analysis supports inter-scale validity, showing items fit well with underlying constructs and a developmental model. A Pearson Separation ratio of 9.67 affirms children can be reliably separated into functional levels based on scores. Note: Test developers require formal training and certification to use this tool. We sponsored the first training session in the U.S. Certified assessors score 20 items on a 4-pt scale from videotaped sessions. Raw scores are converted into unit (or logit) scores (0 to 100). Presently, there is no basis for establishing a minimal clinically meaningful threshold, thus we will use the total Mini AHA unit score.

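### Section 5.2 admits a child with a baseline EBS of 24, who cannot reach the primary outcome, and section 8.1 states a different cut-off

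*Protocol*

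**What the plan says.** Section 5.2 lists among the exclusions a child who "received botulinum toxin in past 3 mos, or baseline EBS score >24 points". Its note repeats the same cut-off and gives the reason: "a child would be precluded from reaching the study primary outcome threshold of a gain of 7 or more EBS points". The note adds that the baseline score is not known until the baseline assessment has been done and scored centrally.

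Section 8.1 says that "children with a baseline EBS of 24 or higher are excluded from the trial in terms of testing the primary efficacy outcome", again because the threshold would be out of reach, and repeats 24 or higher in its next sentence. The same section describes the scale: "The EBS tallies the number of core skills (0 to 30) with the hemiparetic UE". It also asserts that "all infants in the I-ACQUIRE trial and most infants with PAIS will have baseline EBS scores that allow them to acquire this many new skills".

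The outcome is defined in section 3: "A favorable outcome is defined as a gain of ≥ 7 new EBS skills above baseline both at the End of Treatment", and again at 6 months. Section 2.2 reports gains of this size in "subjects with baseline EBS scores as low as 0 and as high as 23".

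Section 6.3 has the site obtain the randomised assignment first and schedule the baseline assessment afterwards. Sections 9.3 and 9.4.2 then restrict the primary (mITT) analysis to randomised children who are still eligible when they attend the baseline assessment.

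**The concern.** Section 5.2 stops one point short of its own purpose. It is meant to remove children for whom the scale ceiling makes the primary outcome impossible, yet it keeps those at 24, for whom it is already impossible. The protocol also states the cut-off in two ways, each of them twice.

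This is more than an editorial slip, because the cut-off is applied after randomisation and decides who enters the primary analysis. A child at 24 is in the mITT set under 5.2 and out of it under 8.1. If the child stays in, a guaranteed failure is counted in whichever arm was assigned, which dilutes the difference between arms. If the question is left open until such a child appears, the choice of analysis set is made after the assignment is known to the family and the treatment team.

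**Working it through.** **Inputs**

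- EBS maximum: 30 (section 8.1)
- Required gain: at least 7 at both post-treatment assessments (section 3)
- Cut-offs: greater than 24 (section 5.2); 24 or higher (section 8.1)
- Assumed success rates: High Dose 70%, Moderate Dose 40% (section 9.2), U&CT up to 15% (section 9.2)
- Planned size: 57 per group before inflation, 80 per group after (sections 9.2 and 4.1)

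**Ceiling arithmetic.** Maximum possible gain = 30 − baseline. Success requires 30 − baseline ≥ 7, that is, baseline ≤ 23.

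| Baseline EBS | Maximum gain | Gain of 7 possible? | Section 5.2 (>24) | Section 8.1 (≥24) |
|---|---|---|---|---|
| 22 | 8 | yes | admitted | admitted |
| 23 | 7 | yes | admitted | admitted |
| 24 | 6 | no | **admitted** | **excluded** |
| 25 | 5 | no | excluded | excluded |
| 30 | 0 | no | excluded | excluded |

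The two rules disagree at exactly one score, 24, and at that score only the section 8.1 rule agrees with the stated reason. The section 8.1 claim that every enrolled infant "will have baseline EBS scores that allow them to acquire this many new skills" is false at 24. The highest successful baseline reported in section 2.2, 23, is the arithmetic limit.

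**Effect on an arm's success rate.** Replacing one child in an arm of 80 by a certain failure costs at most 1/80 = 1.25 points. That maximum applies if the child would otherwise have been sure to succeed. Averaged over the protocol's assumed rates, the loss is p/80:

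- High Dose: 0.70/80 = 0.88 points
- Moderate Dose: 0.40/80 = 0.50 points
- U&CT: 0.15/80 = 0.19 points

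**Effect on power, High versus Moderate Dose.** First, the plan's own figure. The pooled two-proportion formula is n = [z₀.₉₇₅√(2p̄q̄) + z₀.₉₀√(p₁q₁ + p₂q₂)]² / (p₁ − p₂)², where q = 1 − p. With p₁ = 0.70, p₂ = 0.40 and p̄ = 0.55 it gives [1.960 × 0.7036 + 1.282 × 0.6708]² / 0.09 = 55.7, so 56 per group. The protocol states 57, which agrees closely, and 57 × 1.39 = 79.2, so about 80 per group. This sample size does not depend on the EBS cut-off.

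The protocol gives no frequency for a baseline of 24. Suppose k children per 80 in each dose arm are at that score, so that both rates are multiplied by (1 − k/80):

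| k per 80 (assumed) | High | Moderate | Difference | Power, 57 per group | Power, 80 per group |
|---|---|---|---|---|---|
| 0 | 70.0% | 40.0% | 30.0 points | 90.7% | 97.4% |
| 1 | 69.1% | 39.5% | 29.6 points | 89.8% | 97.0% |
| 2 | 68.3% | 39.0% | 29.3 points | 89.0% | 96.6% |
| 4 | 66.5% | 38.0% | 28.5 points | 87.1% | 95.7% |

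**The case against.** The strongest case against is about weight. Only one score is affected, the protocol expects it to be very unusual, and one such child in 80 costs less than one percentage point of power. Baseline EBS is measured before treatment by coders blinded to assignment, so children at 24 should fall across the arms by chance. The result is a slight dilution, without inflation of type I error. The planned continuous EBS sensitivity model would still use whatever gain such a child made. All of this stands, and it limits the numerical harm.

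It can also be said that section 5.2 is the operative criterion, that section 8.1 is narrative, and that its qualifier about testing the primary outcome may mean exclusion from that one analysis and not from the trial. This does not remove the conflict. Section 9.3 uses a single mITT set, defined by eligibility, for all efficacy analyses and has no separate rule for a child at 24. On that reading of 8.1 the child would still be in the primary analysis under 5.2 and 9.3, and out of it under 8.1.

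Finally, the note in 5.2 is literally true for scores of 25 to 30. The fault lies at the boundary, which leaves out the one remaining score to which the same reason applies.

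**Conclusion.** The point holds. On the protocol's own figures a child with a baseline of 24 can gain at most 6 skills, is eligible under section 5.2, and cannot meet the primary outcome in any arm. Section 8.1 excludes that child. Only the 8.1 cut-off fits the stated rationale and the claim that every enrolled infant can gain 7 skills.

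The expected numerical effect is small: at most 1.25 points on an 80-child arm's success rate per affected child. Under the assumed 1 to 4 such children per 80 in each dose arm, High versus Moderate Dose power falls by 0.9 to 3.6 points at 57 per group, or 0.4 to 1.7 points at 80 per group. These power figures rest on an assumed frequency, since the protocol gives none. The ceiling arithmetic and the contradiction rest on no assumption. Correction is required because the threshold is wrong as written and leaves membership of the primary analysis set undetermined.

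**What to change.** In section 5.2, change both mentions of the cut-off to a baseline EBS score of 24 or higher, matching section 8.1. Section 9.3 takes up the criteria by reference, so the change carries through. If the number is repeated there for clarity, it must be identical. In section 8.1, clarify the qualifying phrase so that it is plain whether the child is excluded from the trial or only from the primary test. Under the corrected 5.2 and the present 9.3, the child leaves the mITT set and therefore all efficacy analyses based on it.

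Check whether any child has already been randomised with a baseline of exactly 24. If so, document how that child is handled before outcome data by arm are reviewed, and add a sensitivity analysis that includes the child.

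The cost is a change of a few words, which needs IRB approval like any amendment, and at most a very small number of extra exclusions. The sample size is unaffected.
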